11.5.2 Clinical Laboratory Assessments

Blood and urine samples will be analyzed at a central laboratory, unless otherwise specified. On Day 1, blood samples will be collected before the first dose of the study drug. At all other scheduled visits, these samples will be collected at any time during the visit.

Laboratory test results that are abnormal and considered clinically significant will be reported as AEs (see Section 13.1).

The safety laboratory test panels are shown in Table 11-2.

Table 11-2 Safety Laboratory Test Panels

| Serum Chemistry | Hematology | Urinalysis ^a |
|----------------------------------|---------------------------------------|-------------------------|
| Glucose | Hemoglobin | Urobilinogen |
| Blood urea nitrogen ^b | Platelets | Urine protein |
| Creatinine | Leukocytes | pН |
| Sodium | Differential (percent): | Urine blood |
| Potassium | Eosinophils | Specific gravity |
| Calcium | Basophils | Urine ketones |
| Chloride | Neutrophils | Urine bilirubin |
| Magnesium | Lymphocytes | Urine glucose |
| Bicarbonate | Monocytes | |
| Phosphate | | |
| Total bilirubin | | |
| Direct bilirubin | | |
| Alkaline phosphatase | | |
| Aspartate transaminase | | |
| Alanine transaminase | | |
| Lipase | Coagulation | |
| Gamma-glutamyl transferase | Activated partial thromboplastin time | |
| Protein | Prothrombin time | |
| Albumin | Prothrombin time International | |
| Creatine kinase | Normalized Ratio | |
| Urate | | |

^a If urinalysis results are positive for protein or blood, microscopic examination of urine will be performed and results provided for leukocytes, erythrocytes, crystals, bacteria, and casts.

Clinical laboratory assessments from Screening Visit 1 must have no clinically significant findings that preclude participation in the study, as judged by the investigator, for a subject to proceed to Screening Visit 2 and to receive study drug on Day 1.

Additional tests at screening: The following additional tests will be performed during screening (at Screening Visit 1) to assess eligibility:

- Serum β-human chorionic gonadotropin (β-hCG) test for all biologically female subjects
- Serum follicle-stimulating hormone (FSH) for female subjects who are suspected to be
 postmenopausal; for a subject to be considered of nonchildbearing potential, the serum FSH
 levels will be within the laboratory's range for postmenopausal females
- Serology will include testing for hepatitis B surface antigen, hepatitis C virus antibody, and antibodies against HIV-1/HIV-2. Confirmatory HIV-1/2 Ab differentiation and HIV-1 RNA Qualitative TMA will be performed for positive antibodies against HIV-1/HIV-2. Confirmatory Hep C RNA PCR will be performed for positive hepatitis C virus antibody.
- HbA1c
- Thyroid function test
- Vitamin B12
- Drug and alcohol testing

b If blood urea nitrogen cannot be collected, urea may be substituted.

Drug and alcohol testing: Opioids, methadone, cannabinoids, cocaine, amphetamines/ methamphetamines, barbiturates, and benzodiazepines will be assessed by a urine test at Screening Visit 1 and on Day 1. Alcohol will be assessed by a urine test at Screening Visit 1 and by a urine, blood, or breath test on Day 1 and thereafter. During treatment, drug and alcohol testing will be performed per Table 3-2. Subjects may also undergo random urine drug screening and alcohol testing if deemed appropriate by the investigator.

Drug and alcohol test results must be negative for subjects to receive study drug. However, subjects who have a positive screen for opioids (acute use only) or marijuana at Screening Visit 1 may repeat the test at Screening Visit 2; the second test must be at least 7 days (marijuana) or at least 3 days (opioid) after the first. A positive drug screen for a known prescribed concomitant medication that is not otherwise exclusionary (e.g., benzodiazepines) will not disqualify subjects.

Pregnancy testing for female subjects of childbearing potential (as defined in Section 11.5.6.1):

All biologically female subjects will have a serum pregnancy test at Screening Visit 1. Subsequent pregnancy tests will be performed only for female subjects of childbearing potential (as defined in Section 11.5.6.1) as follows:

- A serum pregnancy test will be performed at the Week 12 or ETT Visit.
- Urine pregnancy tests will be performed at all other visits that require pregnancy testing. At Weeks 3, 7, and 9, the urine pregnancy test may be done either at home or at the study site.

Both the screening (serum) and Day 1 (urine) pregnancy (β -hCG) tests must be negative for a subject to receive study drug. During treatment, if a urine pregnancy test is positive, all study drug dosing will stop, and the pregnancy will be confirmed with a serum β -hCG test. If pregnancy is confirmed, the procedures outlined in Section 11.5.6.2 will be followed.

Additional evaluations: Additional clinical laboratory evaluations will be performed at other times if judged to be clinically appropriate.

Only laboratory tests done in the central laboratory may be used for the safety panels (Table 11-2), the serum pregnancy tests, and the Screening Visit 1 urine drug and alcohol tests; local laboratories and in-clinic (or in-home, where indicated) testing may be used for drug and alcohol tests after Screening Visit 1 and for all urine β -hCG pregnancy tests. In addition, local laboratories may be used at the discretion of the local investigator for management of urgent medical issues. If a local laboratory test value is found to be abnormal and clinically significant, it will be verified by the central laboratory as soon as possible after the investigator becomes aware of the abnormal result. If it is not possible to send a timely specimen to the central laboratory (e.g., the subject was hospitalized elsewhere), the investigator may base the assessment of an AE on the local laboratory value.

11.5.3 Physical Examinations and Vital Signs

A PE of all body systems will be performed at Screening Visit 2 and Day 1. At other visits, symptom-directed PEs can be performed at the discretion of the investigator or healthcare provider. Vital signs assessments will be performed at Screening Visit 1 and at each clinic or home health visit.

A PE includes a review of the following systems: head, neck, and thyroid; eyes, ears, nose, and throat (EENT); respiratory; cardiovascular; lymph nodes; abdomen; skin; musculoskeletal; and neurological. Breast, anorectal, and genital examinations will be performed when medically

indicated. After screening, any clinically significant abnormal findings in a PE will be reported as AEs. If there is a PE finding during a home visit, depending on its severity and at investigator discretion, the subject may be instructed to have a PE or other evaluation in the clinic.

Vital signs include blood pressure (systolic and diastolic), temperature, pulse rate, and respiration rate. The subject will be instructed to rest (seated or supine) for at least 5 minutes before vital signs are assessed.

11.5.4 Electrocardiograms

Standard 12-lead ECGs will be performed in triplicate using a machine with printout. Additional standard 12-lead ECGs will be performed at any other time if clinically indicated. The performance of all ECGs will adhere to the following guidelines. Detailed instructions are provided in the Study Reference Manual:

- The ECG will be done before any other procedures that may affect heart rate, such as blood draws.
- The subject will be instructed to rest (supine) for at least 5 minutes before having an ECG.
- The test should be performed in the supine position.

The acceptable window for the 2- and 4-hour postdose ECGs on Day 1 and Week 5 is \pm 30 minutes relative to the scheduled nominal time.

A printout of the ECG traces will be made for safety review by the investigator and maintained with source documentation. Clinically significant ECG abnormalities occurring during the study through the Safety Follow-up Visit will be recorded as AEs.

To ensure safety of the subjects, a qualified individual at the study site will make comparisons to baseline measurements. If the median QTcF is increased by >60 msec from the baseline or the median absolute QTcF value is ≥500 msec for any scheduled or unscheduled ECGs (performed in triplicate), 2 additional ECGs (performed in triplicate) will be performed approximately 2 to 4 minutes apart to confirm the original measurement. If the median QTcF value from either of these repeated ECGs remains above the threshold value (>60 msec from baseline or ≥500 msec), the subject should discontinue dosing. For safety monitoring after discontinuation, a single ECG will be repeated at least hourly until QTcF values from 2 successive ECGs fall below the threshold value that triggered the repeat measurement.

11.5.5 Columbia Suicide Severity Rating Scale

The C-SSRS will be performed as outlined in Table 3-2.

11.5.6 Contraception and Pregnancy

11.5.6.1 Contraception

Study participation requires compliance with the contraception guidelines outlined below.

Contraception for the couple is waived for the following:

• True abstinence for the subject. The subject must confirm that they will practice true abstinence from Screening Visit 1 through 30 days after the last dose of study drug. True abstinence is important to differentiate from periodic abstinence (e.g., calendar, ovulation,

symptothermal, postovulation methods) and withdrawal, which are not acceptable methods of contraception.

- If the male is infertile (e.g., bilateral orchiectomy). Infertility may be documented through examination of a semen specimen.
- If the female is of non-childbearing potential. To be considered of non-childbearing potential, the female must meet at least 1 of the following criteria:
 - o Postmenopausal: Amenorrheic for at least 12 consecutive months and a serum FSH level within the laboratory's reference range for postmenopausal females
 - o Documented bilateral oophorectomy and/or hysterectomy
- Same biological sex relationships.

For subjects for whom the contraception requirement is not waived, study participation requires a commitment from the subject that at least 1 acceptable method of contraception, as outlined in Table 11-3, is used as a couple from Screening Visit 1 through 30 days after the last dose of study drug.

Table 11-3 Acceptable Methods of Contraception

Subjects and their non-study partners^a

At least 1 of the following acceptable methods must be used as a couple from Screening Visit 1 through 30 days after the last dose of study drug:

- Male vasectomy 6 months or more previously, with a documented negative post-vasectomy semen analysis for sperm^b
- Female bilateral tubal ligation performed at least 6 months previously
- Female continuous use of an intrauterine device for at least 90 days before the first dose of study drug, throughout study drug treatment, and until 30 days after the last dose of study drug.
- Female hormonal contraceptives, if successfully used for at least 60 days before the
 first dose of study drug, throughout study drug treatment, and until 30 days after
 the last dose of study drug.
- Male or female condom (with or without spermicide)^c
- Female barrier contraception (such as diaphragm, cervical cap, or sponge) with spermicide
- ^a Applicable to subjects and their non-study partners of the opposite biological sex for whom the contraception requirement is not waived.
- Medical record documentation of contraception for non-study partners is not required. The subject must confirm that their partner has documented proof, and the subject's confirmation should be documented.
- ^c Female condom cannot be used with male condom due to risk of tearing.

Additional notes:

- If over the course of the study the subject meets the criteria for waiving the contraception requirements, the subject does not need to follow the contraceptive methods listed in Table 11-3.
- Male subjects must not donate sperm from the first study drug dose, throughout the study, and for 90 days following the last dose of study drug.
- Male and female subjects who are not sexually active at the time of screening must agree to follow the contraceptive requirements of this study if they become sexually active.

 If applicable, additional contraception requirements may need to be followed according to local regulations and/or requirements.

Unique situations that may not fall within the above specifications may be discussed with the Vertex medical monitor or designee on an individual basis.

11.5.6.2 Pregnancy

Subjects will be counseled to inform the investigator of any pregnancy that occurs during study treatment and for 90 days after the last dose of tablet study drug.

If a subject, or the female partner of a male subject, becomes pregnant while participating in the study, the study drug will be permanently discontinued immediately. The investigator will (1) notify the medical monitor and Vertex GPS within 24 hours of the site's knowledge of the subject's (or partner's) pregnancy, and (2) send the Pregnancy Information Collection Form to Vertex GPS.

A subject (or their partner, if relevant) who becomes pregnant while on study will be followed until the end of the pregnancy only if on blinded treatment, or if they have been unblinded and have received active drug. The infant will be followed for 1 year after birth, provided informed consent is obtained. A separate ICF will be provided to explain these follow-up activities. Pregnancy itself is not an AE.

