9.1.4 Early Termination of Treatment

If a subject prematurely discontinues study treatment, an Early Termination of Treatment (ETT) Visit should be scheduled as soon as possible after the subject decides to terminate study treatment; the subject will be encouraged to complete the capsule (pregabalin reference or matched placebo) study drug taper.

Subjects who prematurely discontinue treatment will be encouraged to stay in the study, including completing the daily diaries and returning for clinical visits to complete study efficacy assessments (i.e., NPRS, PGIC, DSIS, use of rescue medication, b. These subjects will also be required to complete the Safety Follow-up Visit, approximately $14 (\pm 2)$ days after their last tablet dose of study drug. The assessments performed at the Safety Follow-up Visit are listed in Table 3-2.

If the ETT Visit occurs 14 days or later following the last tablet dose of study drug, then the ETT Visit will replace the Safety Follow-up Visit, and a separate Safety Follow-up Visit will not be required. If the ETT Visit is within a week of any scheduled visit in the Treatment Period, it will replace that scheduled visit, and a separate visit will not be required.

If a subject withdraws consent for the study, no further assessments will be performed. Vertex may retain and continue using the study data and samples after the study ends, and may use the samples and information in the development of the study compound, for other drugs and diagnostics, in publications and presentations, and for educational purposes. If a subject withdraws from the study, the study data and samples collected will remain part of the study (Section 9.10).

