9.4 Study Restrictions

Study restrictions are summarized in Table 9-2. A non-exhaustive list of study restrictions will be provided in the Study Reference Manual.

Table 9-2 Study Restrictions

| Restricted | Timing of Restriction | | |
|---|--|--|--|
| Medication/Food/Activity a | Start | Stop | |
| Other investigational drugs or devices | 30 days before first dose of study drug, 5 half-lives before first dose of study drug, or time determined by local requirements (whichever is longer) | Completion of SFU assessments | |
| Any opioid use for chronic (including neuropathic) pain; for acute use, refer to Section 8.2 and Section 11.5.2 | 3 months before Screening Visit 1 | Completion of Week 12 or ETT Visit assessments | |
| Marijuana or marijuana products | 14 days before first dose of study drug | Completion of Week 12 or ETT Visit assessments | |
| Pregabalin (except use of reference study drug) and gabapentin | 14 days before first dose of study drug | Completion of study drug taper (i.e., 7 days after Week 12 or ETT Visit) | |
| Capsaicin patch | 90 days before first dose of study drug | Completion of Week 12 or ETT Visit assessments | |
| Lamotrigine, carbamazepine, oxcarbazepine, phenytoin, topiramate, valproic acid, mexiletine, and topical agents being prescribed for pain control | 14 days before first dose of study drug | Completion of Week 12 or ETT Visit assessments | |

Table 9-2 Study Restrictions

| Restricted | Timing of Restriction | | |
|--|--|---|--|
| Medication/Food/Activity a | Start | Stop | |
| All SNRIs and tricyclic antidepressants | 14 days before first dose of study drug | Completion of Week 12 or ETT Visit assessments | |
| All other treatments for pain, except acetaminophen (500 mg) and study drug (as outlined in Section 9.4.1), including nonpharmaceutical interventions | 14 days before first dose of study drug | Completion of Week 12 or ETT Visit assessments | |
| Oral steroids | 5 half-lives or 2 days (whichever is longer) before first dose of study drug | Until last dose of study drug is taken | |
| Medications, herbal and dietary supplements (including St. John's wort) known to be moderate or strong inducers of CYP3A | 14 days before first dose of study drug | Completion of SFU assessments | |
| Proton Pump Inhibitors | 72 hours before first dose of study drug | Until last dose of study drug is taken | |
| H2 blockers | 12 hours before each morning dose of study drug | 6 hours after each morning dose of study drug | |

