9.7 Dose Modification for Toxicity

No dose modifications for toxicity are allowed. If any unacceptable toxicity arises, individual subjects will discontinue dosing (Section 9.1.4).

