9.8 Individual Stopping Rules and Precautions

Dosing of study drug in an individual subject will be discontinued if the subject has

- a serious adverse event (SAE) of heart failure that is considered related or possibly related to VX-548 by the investigator or Vertex; or
- an SAE of ventricular arrhythmia that is considered related or possibly related to VX-548 by the investigator or Vertex.

The investigator must immediately notify the Vertex medical monitor if either of the above SAEs occur. All SAEs, regardless of the presumed relationship to study drug, must also be reported to Vertex Global Patient Safety (GPS) within 24 hours (Section 13.1.2).

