9.10 Removal of Subjects

Subjects may withdraw from the study at any time at their own request. Subjects may be withdrawn from study drug treatment at any time at the discretion of the investigator or Vertex for safety, behavior, noncompliance with study procedures, or administrative reasons. A subject who withdraws from study drug treatment will continue to be followed unless the subject withdraws consent.

Subjects who discontinue study treatment early will be encouraged to complete the taper and to continue to return for study efficacy assessments; additional details are provided in Section 9.1.4.

If a subject does not return for a scheduled visit, reasonable effort will be made to contact the subject. In any circumstance, reasonable effort will be made to document subject outcome. The investigator will inquire about the reason for withdrawal, request that the subject return all unused investigational product(s), request that the subject return for a Safety Follow-up Visit, if applicable (see Section 9.1.4) and follow up with the subject regarding any unresolved AEs.

If a subject withdraws consent for the study, no further assessments will be performed. Vertex may retain and continue using the study data and samples after the study ends, and may use the samples and information in the development of the study compound, for other drugs and diagnostics, in publications and presentations, and for education purposes. If a subject withdraws from the study, the study data and samples collected will remain part of the study. A subject will not be able to request the withdrawal of his/her information from the study data. A subject may request destruction of the samples collected from him/her during the study as long as those samples can be identified as his/her samples.

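### At a pregnancy stop the protocol both ends all study drug and tells sites to encourage seven more days of capsules; for the QTcF and cardiac stops it does not say whether the taper applies

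*Protocol*

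**What the plan says.** **Stopping.** Protocol Section 11.5.6.2 covers a pregnancy in a subject or in a male subject's female partner, and says "the study drug will be permanently discontinued immediately". Section 11.5.2 acts earlier, before serum confirmation: "if a urine pregnancy test is positive, all study drug dosing will stop". For a confirmed QTcF threshold, Section 11.5.4 says "the subject should discontinue dosing". Section 9.8 opens its list of two cardiac serious adverse events with "Dosing of study drug in an individual subject will be discontinued if the subject has", and limits it to events judged causally linked, or possibly so, to VX-548.

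**Tapering.** After premature discontinuation, Section 9.1.4 says "the subject will be encouraged to complete the capsule (pregabalin reference or matched placebo) study drug taper", and Table 3-2 footnote c repeats this. Section 9.10 says "Subjects who discontinue study treatment early will be encouraged to complete the taper". None of the three makes an exception by reason for stopping. Section 9.7 refers toxicity stops to Section 9.1.4, and Section 9.10 names safety among the grounds for withdrawing a subject from treatment. Table 9-2 places the end of the taper 7 days after the Week 12 or ETT Visit.

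**The concern.** A site dealing with a pregnancy finds one instruction that ends all dosing and another that has it encourage a further week of capsules. Two sites could each follow a section of the protocol and do opposite things. The capsule may be active pregabalin, and unless the site has been unblinded it will not know. The question affects participant safety and uniform conduct across sites. It does not affect the efficacy estimate.

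**Working it through.** The point turns on wording, so the passages are set side by side after checking the size of the taper.

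**Size of the taper**
- Inputs: 4 days of twice-daily capsules, then 3 days of one capsule daily (Section 9.6, Taper; Table 3-2 footnote d).
- Length: 4 + 3 = 7 days, which reproduces the stated 7 days.
- Capsules: 4 × 2 + 3 × 1 = 11.
- Planned share of subjects with active capsules: 50 / 175 = 28.6% (Table 9-1). Capsules are placebo in all three VX-548 arms (Table 9-3), and no tablets are supplied during the taper (Section 9.1.3).

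**Are capsules covered by the stop rules?** Table 10-1, headed Study Drug, lists pregabalin and its placebo. Sections 9.1.3 and 9.6 name tablet and capsule study drug separately when the distinction matters. Section 11.5.6.2 does so too: its first paragraph specifies tablets when it sets the pregnancy-reporting period, and its second paragraph then stops study drug without that qualifier. Section 11.5.2 stops all of it. On the protocol's own usage, both pregnancy rules include capsules.

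**Does the taper instruction reach safety stops?** Section 9.1.4 schedules the ETT Visit from the subject's own decision to stop, which could suggest elective stops only. But Section 9.7 sends toxicity stops there by number, and Section 9.10 names safety as a ground for withdrawal before giving its taper sentence. The instruction is therefore not confined to elective stops.

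| Stop | Wording | Against the taper text |
|---|---|---|
| Positive urine test (11.5.2) | All study drug dosing stops | Conflicts |
| Pregnancy (11.5.6.2) | Permanent and immediate | Conflicts |
| Confirmed QTcF threshold (11.5.4) | Dosing should be discontinued | Silent on the taper |
| Heart failure or ventricular arrhythmia SAE (9.8) | Dosing discontinued; tied to VX-548 causality | Silent on the taper |
| Unacceptable toxicity (9.7) | Dosing discontinued, with reference to 9.1.4 | No conflict; 9.1.4 is the stated route |

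Neither document contains a rule of precedence.

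**The case against.** The strongest reply is that a specific, directive stop rule naturally overrides general text that only encourages. A subject may decline the taper without breaching anything. This lowers the practical risk but does not remove the conflict, because the encouragement is an instruction to the site. A site that withholds it departs from Section 9.1.4. A site that gives it works against Sections 11.5.2 and 11.5.6.2.

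A second reply is that stopping dosing can mean ending Treatment Period dosing and then following the early-termination procedure, taper included. The cross-reference in Section 9.7 supports this reading. It stands for toxicity stops, and it is why the QTcF and cardiac rules cannot be called contradictory. The cardiac rule also concerns VX-548, which the taper does not supply. A reader might still infer that all these stops clash equally with the taper text, but the wording does not support that. Only the pregnancy rules use terms (all dosing; permanent and immediate) that leave no room for a taper.

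A third reply is that escalation exists. The medical monitor is told at once of the Section 9.8 events and within 24 hours of a pregnancy. Section 10.7.1 allows for unblinding site personnel in a pregnancy, so the capsule's content may become known. This reduces the consequence, but none of these passages says that the monitor decides on the taper.

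Two further inferences are tempting:
- **A count of affected subjects.** One could take a share of the planned 25% dropout (0.25 × 175 = 43.75). But the 25% is an allowance for evaluable sample size, and general toxicity stops are routed to Section 9.1.4 without conflict. The documents give no rate for pregnancies, confirmed QTcF thresholds or the listed cardiac events.
- **A material shift in the treatment-emergent period.** The last-dose rule applies only where there is no Safety Follow-up Visit or equivalent. Section 9.1.4 requires that visit of early discontinuers. Without it, adverse event collection is tied to the last tablet (Section 13.1.1.3).

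**Conclusion.** The point holds for pregnancy: Sections 11.5.2 and 11.5.6.2 cannot be followed together with the taper instruction in Sections 9.1.4 and 9.10 and Table 3-2 footnote c. For Sections 11.5.4 and 9.8 it is a lack of clarity, not a contradiction. What is at issue is 11 capsules over 7 days per affected subject, active for the 29% planned to receive pregabalin.

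The conclusion rests on two readings: that study drug includes capsules, as Table 10-1 and the qualifiers used elsewhere indicate, and that Section 9.1.4 reaches safety stops, as Sections 9.7 and 9.10 indicate. No frequency can be derived from the documents, and the primary analysis is unaffected. It is an internal inconsistency worth correcting because it arises at a safety stop, where a site needs a single instruction.

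**What to change.** Reconcile the passages. In Section 9.1.4, Section 9.10 and Table 3-2 footnote c, state whether the capsule taper applies after a stop under Sections 11.5.2 and 11.5.6.2. Make the same clarification for stops under Sections 11.5.4 and 9.8, and add matching cross-references in those four sections. Which rule applies in each case is the sponsor's medical decision, and none is proposed here.

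The cost is a few sentences in the next amendment or a site clarification letter, with no new procedure and no change to the analysis. Separate fields for last tablet and last capsule dates would add little, because the e-diary already records the date and time of each dose (Section 9.6).
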